9.3 Selection of Study Population

At least 850 subjects with EAD including MCI due to AD and the early stages of mild AD will be enrolled across up to approximately 250 centers worldwide. (revised per Amendment 05) Randomization will be stratified according to region (7 levels), clinical dementia staging, with no more than approximately 25% of the randomized subjects diagnosed with the early stages of mild dementia due to AD, and concurrent AD medication use.

Subjects who do not meet all of the inclusion criteria or who meet any of the exclusion criteria will not be eligible to receive study drug.

9.3.1 Inclusion Criteria

Subjects must meet all of the following criteria to be included in this study:

Core Study

1. MCI due to AD or Mild AD according to the National Institute of Aging – Alzheimer’s Association (NIA-AA) core clinical criteria and must have all of the following at Screening: (revised per Amendment 03)
 - a. MMSE score equal to or greater than 24
 - b. CDR global score of 0.5
 - c. CDR Memory Box score of 0.5 or greater
2. A history of subjective memory decline with gradual onset and slow progression over the last 1 year before Screening; this MUST be corroborated by a study partner
3. Cognitive impairment of at least 1 SD from age-adjusted norms in total recall or delayed recall on the ISLT.
4. Positive biomarker for brain amyloid pathology as indicated by at least 1 of the following:
 - a. PET assessment of amyloid imaging agent uptake into brain. Note: amyloid PET screens will be performed according to local regulatory guidelines and thus may be restricted for those subjects who are not suitable for LP to obtain CSF for testing of eligibility.
 - b. CSF AD assessment (eg, tau: A β (1-42) ratio) (revised per Amendment 03)

NOTE: Subjects may undergo both the amyloid PET and CSF assessments, but need a positive amyloid result in only 1 of the 2 procedures to confirm eligibility. Subjects who consent to amyloid PET or CSF for eligibility purposes are not required to participate in the amyloid PET or CSF longitudinal substudies. Use of a historical amyloid positive PET (conducted within 12 months before the planned date of randomization) is acceptable for determination of eligibility but will not suffice for the baseline assessment if the subject wishes to consent to the amyloid PET longitudinal substudy. The historical imaging data must be made available to the sponsor. Historical CSF samples, if collected, processed, and stored under appropriate conditions and approved by the sponsor, may be analyzed to determine CSF amyloid positivity. (revised per Amendments 03 and 05).
5. Male or female subjects between 50 and 85 years of age, inclusive at the time of consent
6. If receiving an AChEI or memantine or both for AD, must be on a stable dose for at least 12 weeks before Randomization. Treatment-naïve subjects with AD can be entered into the study.
7. Subjects must have been on stable doses of all other (ie, non-AD related) permitted concomitant medications for at least 4 weeks before Randomization, except for medications which are administered as short courses (eg, up to 3 weeks unless discussed and agreed with the medical monitor) of treatment (eg, anti-infectives, oral steroids) or which are to be used on a Pro re nata (PRN) basis. Subjects who require a short course of treatment, such as anti-infectives or oral steroids, may be randomized once the acute illness has completely resolved, even if the concomitant medication continues.
8. Must have an identified study partner (defined as a person able to support the subject for the duration of the study and who spends at least 8 hours per week with the subject). The study partner must be literate and able to provide written informed consent. (revised per Amendment 03) In addition, this person must be willing and able to provide follow-up

information on the subject throughout the course of the study. This person must, in the opinion of the investigator, spend sufficient time with the subject on a regular basis such that they can reliably fulfill the requirements of being a study partner. A study partner need not be living in the same residence with the subject. For such a study partner not residing with the subject, the investigator has to be satisfied that the subject can contact the study partner readily during the times when the study partner is not with the subject. Study partners need to provide input to the following assessments: CDR, FAQ, EQ-5D, QOL-AD, Zarit's Burden Interview, NPI-10, and the clinical assessment of suicidality. Consideration can occur for the investigator to decide whether the study partner can provide information over the telephone or whether the study partner must attend the study visits in person with the subject.

9. Provide written informed consent. Subjects must, in the investigator's judgment, have the capacity to consent (capacity to consent should be determined in accordance with applicable professional standards and local laws/regulations). (revised per Amendment 03)

For inclusion criteria specific to the Extension Phase, refer to [Appendix 5 in Section 12](#).

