- Thyroid stimulating hormone (TSH) above normal range. Other tests of thyroid function with results outside the normal range should only be exclusionary if they are considered clinically significant by the investigator (this applies to all subjects whether or not they are taking thyroid supplements)
 - Abnormally low (below LLN) serum Vitamin B12 levels (if subject is taking Vitamin B12 injections, level should be at or above the LLN). Levels of Vitamin B12 may be confirmed with reflex testing to include methylmalonic acid (MMA) analysis, if available in region. (revised per Amendment 05)
10. Subjects at risk of increased risk of infection, specifically:
- Subjects with chronic viral hepatitis. Subjects with a history of chronic viral hepatitis C may be included if they meet the following requirements:
 - 1) evidence of treatment with direct antiviral combination therapy
 - 2) evidence of sustained virological response at least 12 weeks post-treatmentThe inclusion of subjects with a history of chronic viral hepatitis C must be discussed and agreed with the medical monitor. (revised per Amendment 03)
 - A history of active tuberculosis disease (TB), a history of ophthalmic shingles or a history of ocular herpes simplex virus (HSV) infection (revised per Amendment 03)
 - Any active infection within the last 4 weeks before randomization. For such cases, the timing of randomization can be extended (up to 4 weeks) to allow the infection to resolve
 - Any immunological disease which is not adequately controlled, or which requires treatment with biologic drugs during the study. History of immunoglobulin deficiency or other immunodeficiency disorders (including subjects known to be HIV positive)
11. Have received any live/live attenuated vaccine in the 3 months before randomization
12. Any chronic inflammatory disease that is not adequately controlled or that requires systemic immunosuppressive or immunomodulatory therapy. (revised per Amendment 03)
- NOTE: The following subjects do not need to be excluded:
- Subjects with seasonal or perennial allergic rhinitis, asthma, or chronic obstructive pulmonary disease where the condition is considered to be stable and adequately controlled by inhaled steroids.
 - Hashimoto's thyroiditis but who are stable on thyroid replacement therapy and not on systemic immunosuppressive therapy.

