 - Cutaneous manifestations of immunological disease that do not require systemic immunosuppressive therapy or systemic immunomodulatory therapy (ie, topical steroid treatment is permitted)
13. Any other clinically significant abnormalities, such as:

- Physical examination or vital signs at Screening or Baseline that in the opinion of the investigator require further investigation or treatment or may interfere with study procedures or safety. (revised per Amendment 03)
 - Laboratory tests or ECG at Screening that in the opinion of the investigator require further investigation or treatment or may interfere with study procedures or safety. (revised per Amendment 03)
 - Other medical conditions (eg, cardiac, respiratory, gastrointestinal, psychiatric, renal disease) which are not adequately and stably controlled, or which in the opinion of the investigator(s) could affect the subject's safety or interfere with the study assessments (revised per Amendment 01)
 - Illiteracy, or severe visual or hearing impairment that would prevent the subject from performing psychometric tests accurately
14. A prolonged QTcF interval (QTcF greater than 450 ms according to central reading at Screening). (revised per Amendment 03) If the QTcF machine read is greater than 440 ms on the first single 12-lead ECG, 2 additional 12-lead ECGs will be performed 1 minute apart and the mean of the 3 QTcF values will be calculated. (revised per Amendment 05)
15. Malignant neoplasms within 5 years of Screening (except for basal or squamous cell carcinoma in situ of the skin, or localized prostate cancer in male subjects with treatment cycles completed at least 6 months before Screening). Subjects who had malignant neoplasms but who have had at least 5 years of documented uninterrupted remission before Screening need not be excluded.
16. Hypopigmentation conditions (eg, albinism and vitiligo). Hypopigmentation associated with scarring need not be exclusionary
17. Known or suspected history of drug or alcohol abuse or dependence within 2 years before Screening
18. Taking prohibited medications
19. Have participated in a clinical study involving:
- any therapeutic monoclonal antibody, protein derived from a monoclonal antibody, immunoglobulin therapy, or vaccine within 6 months before Screening for whom it cannot be documented that they were randomized only to placebo or never received study drug
 - elenbecestat

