9.4.7 Prior and Concomitant Therapy

Any medication (including over-the-counter medications) or therapy administered to the subject before the study (within 6 months of randomization) and during the study (starting at the date of informed consent) will be recorded on the Prior & Concomitant Medication eCRF or Non-Pharmacological Procedures eCRF. The investigator will record on the Adverse Event eCRF any AE for which the concomitant medication/therapy was administered. If the concomitant medication/therapy is being administered for a medical condition present at the time of entry into the study, the investigator will record the medical condition on the Medical History and Current Medical Condition eCRF.

Listings of prohibited and permitted drugs are provided in [Appendix 2](#) (Prohibited medications are presented in [Listing 1](#), [Listing 2](#), and [Listing 3](#). Medications that are permitted with restrictions are listed in [Listing 4](#), [Listing 5](#), and [Listing 6](#)).

The following agents are not permitted before randomization (specific time frames are shown below) and until the last visit during the Treatment Period: (revised per Amendment 01)

- a) Immunoglobulin therapy and biologic drugs are not permitted within 6 months before Screening and until the last visit during the Treatment Period (revised per Amendment 01)
- b) Systemic immunosuppressive or immunomodulatory drugs are not permitted for a period of 5 half-lives or 60 days (whichever is longer) before randomization and until the last visit during the Treatment Period (revised per Amendments 01 and 03)
- c) Moderate to strong inhibitors of carboxylesterase 2 (CES2) enzyme activity are not permitted for a period of 5 half-lives or 7 days (whichever is longer) before

randomization and until the last treatment visit. Simvastatin use is permitted only with QD evening administration.

- d) Live/live attenuated vaccines are not permitted within 3 months before randomization and until the last treatment visit (this does not apply to non-live/inactivated vaccines) (revised per Amendment 01)

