Concomitant therapy with AChEI or memantine should only be allowed and/or acceptable for the region or country in which the study is being conducted and should follow the local standard of care for symptomatic treatment (revised per Amendment 01). Subjects who are taking AChEI or memantine will be required to be on a stable dose for at least 12 weeks before randomization. Initiation or termination of therapy or changing dose of AChEIs or memantine during the study should be undertaken in compliance with local standard of care for symptomatic treatment of AD (revised per Amendment 02 and 05). Subjects who start on AChEI or memantine or change their dose during the Treatment Period will be permitted to continue in the study; however, subjects should not undertake cognitive assessments until they have been on a stable dose for at least 4 weeks.

Subjects who are taking other medications will be required to be on a stable dose for at least 4 weeks before randomization, except for medications which are administered as short courses (eg, up to 3 weeks unless discussed and agreed with the medical monitor) of treatment (eg, anti-infectives, oral steroids) or which are to be used on a PRN basis. Concomitant medications (including opiates and short-term use of benzodiazepines) which are used on a PRN basis and which are central nervous system (CNS) active and may affect cognitive function are not permitted during a period of 72 hours before cognitive testing. (revised per Amendment 03)

For subjects who undergo an LP for collection of CSF: Subjects who are on anticoagulants may have a variable dose but should have stable anticoagulation control for at least 4 weeks before the LP procedure. Subjects may be required to stop their anticoagulant medication before CSF collection and then restart this medication after the LP procedure, as per local guidelines.

Either aspirin or clopidogrel (or any other antiplatelet drug that is not aspirin) is permitted in all subjects. Aspirin and clopidogrel (or any other antiplatelet drug which is not aspirin) in combination are also permitted but subjects who are on such a combination of antiplatelet drugs may be required to stop 1 or more of these antiplatelet drugs before the LP procedure and restart after the LP as per local guidelines.

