Appendix 2 List of Permitted and Prohibited Prior/Concomitant Medications

Prohibited medications are shown in [Listing 1](#), [Listing 2](#), and [Listing 3](#). Medications permitted with restrictions are listed in [Listing 4](#), [Listing 5](#), and [Listing 6](#). These may not be all-inclusive listings. Please contact the medical monitor(s) if the investigators have any questions or concerns regarding any medication not listed that your subjects may be taking before enrollment or start during the course of the E2609-G000-302 study.

Antibiotics, analgesics, and anti-inflammatory drugs intended for short courses of treatment are permitted and do not need to follow the restrictions of [Listing 6](#) for a stable dose of 4 weeks before Baseline. If these medications may affect cognitive function but the medications are clinically indicated, then cognitive testing should not take place until at least 72 hours after the last dose of the course of treatment.

Prohibited Prior/Concomitant Medications

Listing 1 Prohibited Medications Within 5 Half Lives or 7 Days, Whichever is Longer, Before Randomization and Until the Last Visit During the Treatment Period

Moderate to Strong Inhibitors of Carboxylesterase 2 (CES2) Enzyme Activity
Generic name
Loperamide
Orlistat
Telmisartan
Fenofibrate
Carvedilol
Manidipine
Diltiazem
Verapamil
Itraconazole (revised per Amendment 04)

NOTE: Simvastatin use is permitted only with once daily evening administration.

Listing 2 Prohibited Medications Within 5 Half Lives or 60 Days, Whichever is Longer, Before Baseline and Until the Last Visit During the Treatment Period

Systemic Immunosuppressants^a and Immunomodulatory Drugs (revised per Amendments 01 and 03)	
Prednisolone	Deltasone, Prednicot, Prednisone Intensol, Rayos, Sterapred, Sterapred DS
Methylprednisolone	Medrol, Meprolone
Dexamethasone	Decadron, Dexasone, Diodex, Hexadrol, Maxidex
Azathioprine	Azasan, Imur
Mycophenolate	CellCept, Myfortic
Fingolimod	Gilenya
Methotrexate	Trexall
Ciclosporine	Gengraf, Neoral

Prohibited Medications Within 6 Months Before Screening and Until the Last Visit During the Treatment Period (revised per Amendment 01)

Immunoglobulin Therapy and Biologic Drugs (revised per Amendment 01)	
Ranibizumab	Lucentis
Bevacizumab	Avastin
Infliximab	Remicade
Etanercept	Enbrel
Adalimumab	Humira
Omalizumab	Xolair
Efalizumab	Raptiva

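### Inclusion criterion 7 allows randomization during a continuing course of oral steroids that the protocol prohibits elsewhere

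*Protocol*

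**What the plan says.** Inclusion criterion 7 (9.3.1) requires stable doses of permitted non-AD medication for 4 weeks before randomization. It exempts short courses, with oral steroids as one of its two examples. It then adds that subjects needing a short course, "such as anti-infectives or oral steroids, may be randomized once the acute illness has completely resolved, even if the concomitant medication continues".

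Section 9.4.7 gives the same example when it exempts short courses from the 4-week rule: "of treatment (eg, anti-infectives, oral steroids) or which are to be used on a PRN basis".

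Item (b) of the same section says: "Systemic immunosuppressive or immunomodulatory drugs are not permitted for a period of 5 half-lives or 60 days (whichever is longer) before randomization". The ban runs on to the last visit of the Treatment Period.

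Listing 2 in Appendix 2 carries the matching heading, "Prohibited Medications Within 5 Half Lives or 60 Days, Whichever is Longer, Before Baseline and Until the Last Visit During the Treatment Period", and names prednisolone, methylprednisolone and dexamethasone. Its footnote exempts topical, ocular and inhaled formulations only.

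Exclusion 18 reads "Taking prohibited medications". Section 9.3 makes every exclusion binding: subjects "who meet any of the exclusion criteria will not be eligible to receive study drug".

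The opening text of Appendix 2 adds that "anti-inflammatory drugs intended for short courses of treatment are permitted and do not need to follow the restrictions of" Listing 6. It does not mention Listing 2.

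**The concern.** The protocol gives two opposite answers about the same subject. Someone whose acute illness has cleared but who is still finishing a course of oral prednisolone may be randomized according to inclusion 7, and is excluded according to 9.4.7(b), Listing 2 and exclusion 18. Formally the exclusion wins. The explicit sentence that site staff read in the inclusion list says the reverse, and the short-course sentence in Appendix 2 could be taken to support it.

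A site acting in good faith on inclusion 7 would start study drug in a subject taking what the protocol itself lists as a systemic immunosuppressant. Section 7.1 reports some reduction in CD4 counts by Day 15 at 50 to 100 mg in the multiple-dose study, and this trial gives 50 mg daily. The washout keeps the two exposures apart, and inclusion 7 waives it. Each such randomization would also be an eligibility deviation that the protocol's own wording had produced.

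**Working it through.** No sample size, power or error rate is involved. The check is a side-by-side reading, with simple arithmetic on days.

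**Step 1. Apply each rule to one subject: acute illness resolved, oral prednisolone continuing on the day of randomization.**

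| Provision | Answer for this subject | Steroid-free days required |
|---|---|---|
| Inclusion 7, second sentence | may be randomized | 0 |
| 9.4.7(b) | not permitted | at least 60 |
| Listing 2 (prednisolone named) | not permitted | at least 60 |
| Exclusion 18 with Section 9.3 | ineligible | drug must not be in use |

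A subject who has recently finished a course is not taking the drug, so exclusion 18 does not apply by its wording, but 9.4.7(b) still bars randomization.

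**Step 2. Look for an exemption that would reconcile the rules.**

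- The word permitted in the first sentence of inclusion 7 does not help. The same sentence gives oral steroids as its example, and the second sentence names them again.
- The 9.4.7 paragraph on other medications waives the 4-week stable-dose rule only. It does not touch item (b).
- The Appendix 2 sentence waives Listing 6 only. It names neither steroids nor Listing 2.
- The Listing 2 footnote exempts by route of administration. Oral use is not among the exempt routes, and course length is not mentioned.

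No text releases a short oral course from the 60-day rule.

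**Step 3. See whether other criteria stop the same subject.**

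- Exclusion 10 covers "Any active infection within the last 4 weeks before randomization", so it does not reach a non-infectious illness.
- Exclusion 12 covers chronic inflammatory disease, so it does not reach an acute episode.
- The lymphocyte count limit at screening (exclusion 9) and the interruption rule below 800/mm³ (9.3.3) act on the count. They do not enforce a washout.

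A subject treated with oral steroids for an acute, non-infectious illness, with a normal lymphocyte count, passes all of these.

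**Step 4. Check that enforcing the washout is workable.** Section 9.1.1.1 permits re-screening. It keeps Tier 1 to 3 results valid for 96 days, and MRI, CSF and study PET results for 90 days. Inclusion 7 gives up to 3 weeks as the example length of a short course.

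- Course plus washout: 21 + 60 = 81 days.
- Margin against 90 days: 90 − 81 = 9 days.
- Margin against 96 days: 96 − 81 = 15 days.
- The Prerandomization Phase allows 50 + 30 = 80 days, so a full 3-week course started during screening overruns it and needs re-screening.

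Earlier results can carry over, but the margin is small. Any days between the assessment and the start of the course use it up.

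**The case against.** The best reply is that the sponsor meant short courses to be an exception. Inclusion 7 is the more specific rule, 9.4.7 repeats the example, and the Appendix 2 sentence stands ahead of all the listings and says short-course anti-inflammatory drugs are allowed. On that reading the 60-day ban is aimed at chronic immunosuppression, and deleting the example would tighten eligibility beyond what was intended.

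Part of this stands. The document does not prove intent, and the 9.4.7 paragraph on its own creates no permission to randomize. The direct conflict comes from the second sentence of inclusion 7. But no text writes the exception into 9.4.7(b) or Listing 2, and the footnote shows that where the authors spared steroids under Listing 2 they did so by route. If an exception was intended, 9.4.7(b) and Listing 2 are wrong as written, so one text has to change either way.

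A second reply is that the practical effect is small. Eligibility and medications are reviewed again at Visit 2, exclusion 18 applies, and lymphocytes are monitored. These controls do limit the risk. However, the Visit 2 review uses the same contradictory criteria, and the protocol offers no data on combined use with steroids that would show the overlap to be harmless. It is fair that the number affected is unknown and probably small.

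It is also true that enforcing 9.4.7(b) makes a short oral steroid course during the 24 months of treatment a use of a prohibited drug. That follows from 9.4.7(b) as it stands and is not created by correcting inclusion 7.

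**Conclusion.** The point holds. Inclusion 7 states a permission that is false for the steroids named in Listing 2. The discrepancy is 0 days against at least 60 days of steroid-free time before randomization. How many subjects it would affect cannot be derived from the protocol. No bias in the CDR-SB comparison and no loss of power is claimed. The weight lies in eligibility and safety, and the matter should be corrected.

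The conclusion rests on two readings: that the oral steroids in inclusion 7 include the drugs named in Listing 2, and that an exclusion overrides an inclusion permission, as Section 9.3 states. It concerns steroids only. The anti-infective half of the sentence does not conflict with Listing 2.

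**What to change.** Delete oral steroids from both places in inclusion 7 and from the short-course examples in 9.4.7. Make the same deletions in the Synopsis (inclusion 7 and concomitant therapy) if its current text still carries them; the copy supplied lacks the Amendment 06 wording and may predate the current body text. Add to Appendix 2 that its short-course sentence does not apply to drugs in Listing 2.

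If the sponsor did intend a short-course exception, it has to be written into 9.4.7(b) and Listing 2 with a stated washout. Deletion is preferable because it matches the prohibition that already controls and is the safer option.

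The change needs no new data. Subjects who need a steroid course during screening will be delayed or re-screened, with results reused where their dates fall within the 90- and 96-day limits.
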